3. STUDY DESIGN

This is a randomized, double-blind, placebo-controlled, SAD study conducted at one study center in the US.

Four (4) cohorts of either 6 subjects (Cohort 1 [4 active and 2 placebo]) or 5 subjects (Cohorts 2, 3, and 4 [4 active and 1 placebo]) are planned for evaluation. In each cohort, subjects will be randomized to receive a single IV infusion of xisomab 3G3 or placebo. In each cohort, at least 30% of the subjects were to be of a race/ethnicity minority group. An attempt will be made to include at least 2 females per cohort. Subjects will participate in only one cohort.

Two (2) sentinel subjects will be dosed (one placebo, one active) in Cohort 1 and data will be collected through Day 8. The next subject in the cohort will be dosed after evaluation of the sentinel subjects' Day 8 safety data. Each subject following these sentinel subjects will be dosed with an interval of 24-hours between subjects. Subjects in Cohorts 2, 3, and 4 will be dosed at an interval of 24 hours between subjects.

Screening of subjects will occur within 28 days prior to dosing.

Subjects will receive a single IV infusion dose of the assigned formulation (xisomab 3G3 or placebo) on the morning of Day 1.

Subjects will be housed on Day -1, at the time indicated by the Clinical Research Unit (CRU), until after the 24-hour blood draw and/or study procedures. Subjects will only be discharged if the prothrombin time (PT)/international normalized ratio (INR) values are ≤ 3.5 and judged not clinically significant by the PI or designee. Subjects will need to return to the CRU at least 2 days after discharge to confirm the PT/INR values.

Blood samples will also be collected for the PK (free xisomab 3G3) and PD (aPTT) assessments of xisomab 3G3 at scheduled time points for at least 672 hours postdose. The planned time points are at predose, and at 0.083, 0.25, 0.5, 1, 3, 8, 24, 72, 120, 168, 216, 336, 504, and 672 hours after xisomab 3G3 start of infusion. Following the 672-hour time point, sample collection for PK and PD assessments will continue every 7 days (± 2 days) until aPTT values return within $\pm 10\%$ of the baseline value or the normal range.

Safety and tolerability will be monitored throughout the study by repeated clinical and laboratory evaluations.

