4. ANALYSIS POPULATIONS

4.1 Analysis Populations

Safety Population

The safety population will include all subjects who received at least one dose of study drug (active or placebo).

Pharmacokinetic Population

The PK population will include data from all subjects who received at least one dose of active study drug and completed at least one PK blood draw resulting in at least one quantifiable plasma concentration. Samples from all subjects will be assayed even if the subjects do not complete the study. All subjects who comply sufficiently with the protocol and display an evaluable PK profile (e.g., exposure to treatment, availability of measurements and absence of major protocol violations) will be included in the PK parameter summary and statistical analyses.

Pharmacodynamic Population

The PD population will include all subjects who received the study drug (active or placebo) and have at least one predose and one postdose quantifiable PD biomarker value. All subjects who comply sufficiently with the protocol and display an evaluable PD profile will be used for summary statistics.

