7.5 Data Summarization and Presentation

aPTT values will be extracted from the clinical laboratory database and descriptive statistics will be generated using SAS® version 9.3 or higher. A table will be presented for the aPTT change from baseline with descriptive statistics. Change from baseline will be calculated by subtracting the predose aPTT value from the postdose aPTT value at each time point. The mean change from baseline will be calculated using the individual change from baseline values. If change from baseline results in a negative value, this value will be set to '0' for the calculation of the summary statistics.

aPTT values will be listed and summarized by treatment and time points for all subjects in the PD Population. aPTT values will be presented with the same level of precision as received from the clinical laboratory database. Summary statistics, including n, Mean, SD, CV%, SEM, minimum, median, and maximum will be

calculated for all nominal values time points. Excluded subjects will be included in the aPPT values tables, but will be excluded from the summary statistics and noted as such in the tables.

Mean and individual aPTT values-time and change from baseline-time profiles will be presented on linear scale. Linear mean plots will be presented with and without SD.

The level of precision for the aPPT values summary statistic will be presented as follows:

- minimum/maximum: in same precision as in the clinical laboratory database
- Mean/median: in one more level of precision than minimum/maximum
- SD/SEM: in one more level of precision than Mean/median
- n will be presented as an integer
- CV% will be presented to the nearest tenth

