10.1 In-text Summary Tables and Figures

The following is a list of table and figure titles that will be included in the text of the CSR. Tables and figures will be numbered appropriately during compilation of the CSR.

Section 10:

Table 10-1 Disposition Summary

Section 11:

- Table 11-1 Demographic Summary
- Table 11-2 Summary of Plasma Xisomab 3G3 Pharmacokinetics Following a Single IV Infusion of 0.1, 0.5, 2, and 5 mg/kg Xisomab 3G3
- Figure 11-1 Arithmetic Mean Plasma Xisomab 3G3 Concentration -Time Profiles Following a Single IV Infusion of 0.1, 0.5, 2, and 5 mg/kg Xisomab 3G3 (Linear Scale)
- Figure 11-2 Arithmetic Mean aPPT Values Versus Time Following a Single IV Infusion of 0.1, 0.5, 2, and 5 mg/kg Xisomab 3G3 and Pooled Placebo (Linear Scale)
- Figure 11-3 Arithmetic Mean aPPT Change From Baseline Versus Time Following a Single IV Infusion of 0.1, 0.5, 2, and 5 mg/kg Xisomab 3G3 and Pooled Placebo (Linear Scale)

Section 12:

Table 12-1 Adverse Event Frequency by Treatment - Number of Subjects Reporting the Event (% of Subjects Dosed)

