14.2.3 Plasma Pharmacodynamic aPTT Table

Table 14.2.3.1 Mean aPTT Values (sec) and Mean Change from Baseline aPTT Values (sec) Following a Single IV Infusion of 0.1, 0.5, 2.0, and 5 mg/kg Xisomab 3G3 and Placebo (Pharmacodynamic Population)

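### The SAP plans no estimate of the aPTT difference from pooled placebo and no interval, and flooring negative changes at zero means the planned change summaries cannot supply an unbiased one

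*SAP*

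**What the plan says.** SAP 3 describes the design: "This is a randomized, double-blind, placebo-controlled, SAD study conducted at one study center in the US". Assessing PD, with aPTT as the marker, is a secondary objective (SAP 2.1). SAP 4.1 puts placebo subjects in the PD population, and SAP 7.1 samples all subjects at predose and 14 postdose times to 672 hours.

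SAP 7.5 plans two kinds of summary.

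- Raw values: "aPTT values will be listed and summarized by treatment and time points for all subjects in the PD Population". The statistics are given as "Summary statistics, including n, Mean, SD, CV%, SEM, minimum, median, and maximum will be" calculated at each nominal time.
- Changes: "Change from baseline will be calculated by subtracting the predose aPTT value from the postdose aPTT value at each time point". It then adds: "If change from baseline results in a negative value, this value will be set to '0' for the calculation of the summary statistics".

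Table 14.2.3.1 is titled "Mean aPTT Values (sec) and Mean Change from Baseline aPTT Values (sec) Following a Single IV Infusion" and goes on to name the four doses and placebo. Its shell has arm columns for values and changes, a note to add the fourth dose, and no difference column or interval. Placebo is also plotted with the doses; the title of Figure 11-3 includes "Change From Baseline Versus Time Following a Single IV Infusion of 0.1, 0.5, 2, and 5 mg/kg Xisomab 3G3 and Pooled Placebo". Protocol 12.1.6 asks only for a listing and graphs of aPTT, with PD parameters optional.

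The statements that rule out inferential statistics (Protocol 12.1.3, SAP 8) concern safety data. They do not mention PD.

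**The concern.** A mean change within one arm is the drug effect plus whatever else moves aPTT between the predose sample and the later time. The placebo group is there to measure the second part. The plan prints it beside the doses but never subtracts it, and gives no measure of uncertainty for the difference.

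This matters most where the effect is small. Protocol 8.4.2 chose 0.1 mg/kg as a dose expected to do little, so that arm is the hardest to tell from placebo by eye.

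The obvious remedy, subtracting one printed mean change from another, fails because of the zero floor. The floor acts hardest on placebo and low-dose subjects, whose changes scatter around zero.

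Protocol 8.4.1 says the study should help choose dose levels and intervals for Phase 2. SAP 1 treats analyses outside the plan as out of scope, to be described in the study report, so a contrast added later would not be prespecified.

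**Working it through.** **Inputs.** Arm sizes: Protocol 10.1 and 10.3.1. Sampling times: SAP 7.1. Zero floor: SAP 7.5. The documents give no SD of aPTT change, no within-subject correlation and no size for any shared drift. Results are therefore in units of the SD of change, or for assumed SDs of 1, 2 and 3 s; the shifts and effects below are also assumptions.

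**1. The plan's own figure.** (4 + 2) + 3 × (4 + 1) = 21, which is 16 active and 5 placebo. This matches the planned enrolment. Protocol 12.1.1 says the size had no statistical basis, so there is no power figure to test.

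**2. What a within-arm change contains.** Write change = drug effect + shared shift + error. With a shift of +1 s and a true effect of 2 s, the arm's mean change is 3 s, placebo's is 1 s, and the untruncated contrast is 3 − 1 = 2 s. The shift cancels only on subtraction.

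**3. What the zero floor does.** For a change X ~ N(m, s), the mean after flooring is E[max(0, X)] = mΦ(m/s) + sφ(m/s). At m = 0 this is s × 0.399, about 0.40 SD instead of 0. With no shared shift:

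| Assumed SD | Placebo mean (true 0) | Arm mean (true 2 s) | Contrast (true 2 s) | Contrast (true 10 s) |
|---|---|---|---|---|
| 1 s | 0.40 | 2.01 | 1.61 | 9.60 |
| 2 s | 0.80 | 2.17 | 1.37 | 9.20 |
| 3 s | 1.20 | 2.45 | 1.26 | 8.80 |

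With a shared shift of −1 s, a true 2 s effect shows as 1.00 s at all three SDs.

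**4. Whether the raw-value summaries can replace it.** If n is constant over time, differences of raw means give an untruncated point estimate. An interval needs the SD of change, which depends on the within-subject correlation, and that is not printed. The Table 14.2.3.1 shell also has no SEM row, although its notes mention SEM. A reader would have to reanalyse the individual values in Appendix 16.2.6.2.

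**5. How wide the missing interval would be.** One dose against pooled placebo: SE = SD × √(1/4 + 1/5) = 0.671 SD.

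- SD from those two arms (7 df): 2.365 × 0.671 = 1.59 SD, which is 1.6, 3.2 or 4.8 s for SDs of 1, 2 or 3 s.
- SD pooled over five arms (16 df): 2.120 × 0.671 = 1.42 SD.
- Baseline-adjusted (21 − 5 − 1 = 15 df), with equal variances before and after dosing: 2.131 × 0.671 × √((1 + ρ)/2) = 1.24, 1.32 or 1.38 SD for assumed ρ of 0.5, 0.7 or 0.85. Expected chance baseline imbalance widens these by about 3.5%, so the range becomes about 1.28 to 1.42.

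For comparison, one arm's mean change has half-width 3.182/√4 = 1.59 SD on its own 3 df, and 2.131/√4 = 1.07 SD on 15 df.

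**The case against.** The strongest reply is that this is a descriptive 21-subject study. The protocol asks only that aPTT be listed and graphed, and the SAP already goes further. Placebo sits beside every dose, so a sizeable drift would be visible. The proposed model gives 4 doses × 14 postdose times = 56 intervals from 4 against 5 subjects. It also borrows error variance across arms that may differ, since Protocol 8.4.2 expects the maximum effect at or below 1 mg/kg. Much of this stands: it limits the weight of the point and argues for estimation without tests. It does not answer the zero floor, and it does not turn a side-by-side display into an estimate with an interval.

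A reader might infer four stronger things that the documents do not support.

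- **That the control is unused, or that only changes are reported.** Placebo is in the PD population, the table and the figures, and raw aPTT is summarised too.
- **That subtracting placebo gives a tighter interval.** At equal degrees of freedom the single arm is narrower (1.07 SD against 1.24 to 1.38 SD). An unpooled contrast (1.59 SD) only equals the unpooled single arm. Any apparent gain comes from pooling variance and from assumed correlations.
- **That the contrast removes all variation over time.** Subjects after the sentinels are dosed 24 hours apart, cohorts are separated by a Day 29 review, and Cohorts 2 to 4 each have one concurrent placebo subject. Only elapsed-time effects common to cohorts cancel; day- or run-specific variation does not.
- **That the lowest-dose effect is known to be as small as the shared drift, or that seconds conflict with the recovery rule.** No document gives a size for the drift. The recovery rule has two limbs, 10% of baseline or the reference range of 23 to 32 s, and it governs follow-up sampling rather than an analysis endpoint.

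**Conclusion.** The point holds as a gap in estimation. No dose-versus-placebo estimate or interval is planned for aPTT, nothing in the documents rules one out for PD, and the planned change summaries would bias one built from them.

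The floor raises the mean by about 0.40 SD in any arm with no true change. Under the assumed SDs and no shared shift, it understates a 2 s contrast by 0.39 to 0.74 s and a 10 s contrast by 0.4 to 1.2 s. These sizes rest on normally distributed changes with equal SD in both arms. The bias in seconds for this trial cannot be stated from the documents, and nor can the size of any shared drift.

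In a descriptive first-in-human study this ranks between optional and advisable. It limits how the PD results can be read, chiefly at the lowest dose, and does not invalidate the planned display.

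**What to change.** Add to SAP 7.5: at each nominal postdose time to 672 hours, fit an ANCOVA of log(aPTT) on log(baseline aPTT) and treatment (pooled placebo, A to D) in the PD population, using untruncated values. Report each dose's adjusted ratio to pooled placebo with a 95% CI and no hypothesis tests. A simpler check is the untruncated dose-minus-placebo difference in change with its CI.

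Keep Table 14.2.3.1, but compute its change statistics, and the change figures drawn from it, without the zero floor. Add ratio to baseline beside seconds, which also lines up with the 10% limb of the recovery rule.

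The cost is one SAP paragraph, one table and a shell edit. Sampling and conduct do not change, and Protocol 12.1 already allows the SAP to add analyses. State the limits in the text:

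- A common slope and variance across arms are assumed; compare the arm SDs on the log scale.
- The intervals are wide at 4 against 5.
- Pooled placebo is only partly concurrent (2, 1, 1 and 1 subjects by cohort), so day- and run-specific variation remains.

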2.2 Endpoints

The primary endpoints of the study will be the number and severity of treatmentemergent adverse events (TEAEs) following single doses of xisomab 3G3 and placebo. Other safety endpoints include clinical laboratories, vital signs, electrocardiograms, physical examinations, and immunogenicity.

- The following PK parameters of free xisomab 3G3 in plasma following single IV dose, will be calculated, as appropriate: AUC0-t, AUC0-inf, AUC%extrap, Cmax, Tmax, Kel, T½, MRT, CL, and Vss.
- aPTT values will be listed with descriptive statistics and presented graphically.

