All coagulation results for PD endpoint aPTT will be listed with the clinical laboratory results and included in the out-of-range table, but for the time points outlined in Section 7.1 summaries will not be included in the clinical laboratory summary tables.

For all numeric laboratory values, descriptive statistics will be presented for each laboratory test by assessment time point and treatment (pooled placebo and xisomab 3G3 dose levels). Change from baseline will be summarized in a similar manner. Baseline is defined as the result closest and prior to dose which may include unscheduled or recheck results. This will typically be the result collected on Day -1.

Postdose unscheduled events or rechecks will not be included in summaries. Similarly early termination results will not be included in summaries.

For each laboratory test, a shift table will be developed to compare the frequency of the results at baseline (above normal, normal, or below normal) with the respective postdose results. For urinalysis tests, the categories are normal and outside normal.

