11.3 Section 14 Summary Tables Shells

Part 1 of X

Table 14.1.1 Summary of Disposition (Safety Population)

Treatment

Disposition	A	В	С	D 1	Pooled Placebo	Pooled Active	Overall
Dosed	XX	XX	XX	XX	XX	XX	XX
Completed	XX	XX	XX	XX	XX	XX	XX
Discontinued Early	X	X	X	X	X	X	X
<reason></reason>	X	X	X	X	X	X	X

Note: Treatment A: < >
 Treatment B: < >
 Treatment C: < >
 Treatment D: < >

Program: /AAXXXXX/ECR/sas_prg/stsas/tab prog_name.sas DDMMMYYYY HH:MM

Table 14.1.2 Demographic Summary (Safety Population)

				Treatment				
Trait		Α	В	C	D	Pooled Placebo	Pooled Active	Overall
Sex	Male Female	X (XX.X%) X (XX.X%)	X (XX.X%) X (XX.X%)	X (XX.X%) X (XX.X%)	X (XX.X%) X (XX.X%)	, , , , , , , , , , , , , , , , , , , ,	, ,	X (XX.X%) X (XX.X%)
Race	American Indian Asian Black	X (XX.X%) X (XX.X%) X (XX.X%)	X (XX.X%) X (XX.X%) X (XX.X%)	X (XX.X%) X (XX.X%) X (XX.X%)	X (XX.X%)	X (XX.X%)	X (XX.X%) X (XX.X%) X (XX.X%)	X (XX.X%) X (XX.X%) X (XX.X%)
Ethnicity	Hispanic or Latino Not Hispanic or Latino		X (XX.X%) X (XX.X%)				·	X (XX.X%) X (XX.X%)
Age* (yrs)	n Mean SD Minimum Median Maximum	X X.X X.XX XX XX XX	X X.X X.XX XX XX XX	X X.X X.XX XX XX XX	X X.X X.XX XX XX XX	X X.X X.XX XX XX X.X	X X.X X.XX XX XX XX	X X.X X.XX XX XX XX
Weight (kg)	n Mean SD Minimum Median Maximum	X X.X X.XX XX XX X.X	X X.X X.XX XX XX X.X	X X.X X.XX XX XX XX	X X.X X.XX XX XX XX	X X.X X.XX XX XX X.X	X X.X X.XX XX XX X.X	X X.X X.XX XX XX XX

Programmer Note: Add Height (cm) and Body Mass Index (kg/m2) to the following page

Note: Treatment A: < >
Treatment B: < >
Treatment C: < >
Treatment D: < >

*Age is calculated at the time of dosing and reported as an

integer. Program:

Tables 14.2.1.1 through 14.2.1.5 and Appendix 16.2.6.2 and 16.2.6.4 will be in the following format:

Table 14.2.1.1 Plasma Xisomab 3G3 Concentrations (ng/mL) Following a Single IV Infusion of 0.1 mg/kg Xisomab 3G3 (Treatment A) (Pharmacokinetic Population)

Subject				Samp	le Times	(hr)			
Number	Predose	XX	XX	XX	XX	XX	XX	XX	XX
X	BLQ	XX	XX	XX	XX	XX	XX	XX	XX
X	BLQ	XX	XX	XX	XX	XX	XX	XX	XX
X	BLQ	XX	XX	XX	XX	XX	XX	XX	XX
n	XX	XX	XX	XX	XX	XX	XX	XX	XX
Mean	XX.X	XX.X	XX.X	XX.X	XX.X	XX.X	XX.X	XX.X	XX.X
SD	XX.XX	XX.XX	XX.XX	XX.XX	XX.XX	XX.XX	XX.XX	XX.XX	XX.XX
CV%		XX.X	XX.X	XX.X	XX.X	XX.X	XX.X	XX.X	XX.X
SEM	XX.XX	XX.XX	XX.XX	XX.XX	XX.XX	XX.XX	XX.XX	XX.XX	XX.XX
Minimum	XX	XX	XX	XX	XX	XX	XX	XX	XX
Median	XX.X	XX.X	XX.X	XX.X	XX.X	XX.X	XX.X	XX.X	XX.X
Maximum	XX	XX	XX	XX	XX	XX	XX	XX	XX

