Programmer note: The following footnote only presented on Coagulation summary tables

Change from baseline summaries for aPTT associated with PD time points can be found Table 14.X.X.X.

Note: Treatment A: < >
Treatment B: < >
Treatment C: < >
Treatment D: < >

Baseline is the last predose measurement.

Program: /CAXXXXX/ECR/sas prg/stsas/tab programname.sas DDMMMYYYY HH:MM

Page 1 of X

Tables 14.3.5.6 (hematology), 14.3.5.9 (urinalysis), and 14.3.5.12 (coagulation & bleeding time) will resemble 14.3.5.3

Page 1 of X Table 14.3.5.3 Clinical Laboratory Shift From Baseline - Serum Chemistry (Safety Population)

			Baseline L		Baseline N		Bas	eline	Н		
		_		Postdo	se	Po	stdos	е		Postdo	ose
Laboratory Test (units)	Treatment	Time Point	L	N	Н	L	N	Н	L	N	Н
Testname (unit)	Х	Day 1 Hour 8	Х	XX	X	X	XX	Х	Х	XX	Х
		Day 2	X	XX	X	X	XX	X	X	XX	X
		Day 8	Χ	XX	X	X	XX	X	X	XX	X
		Day 29	X	XX	X	X	XX	X	X	XX	X
		Follow-up	Χ	XX	X	X	XX	X	X	XX	X
Testname (unit)	X	Day 1 Hour 8	Х	XX	X	Х	XX	X	X	XX	X
		Day 2	Χ	XX	X	X	XX	X	X	XX	X
		Day 8	Χ	XX	X	X	XX	X	X	XX	X
		Day 29	Χ	XX	X	X	XX	X	X	XX	X
		Follow-up	X	XX	X	X	XX	X	X	XX	Χ

Programmer note: Time points are Day 1 Hour 8, Day 2, Day 8, Day 29, and Follow-up. Coagulation time points are Day 1 Hour 1, Day 2, Day 4, Day 8, Day 29, and Follow-up. aPTT samples for PD time points are not presented here. Bleeding time is presented with coagulation with time points Day 1 Hour 1 and Day 2.

Programmer note: For urinalysis, the following footnote is used since the categories of N and O will be used instead of L, N, and H

Note: N = Within reference range, O = Outside reference range

Note: Treatment A: < >
Treatment B: < >

Treatment C: < >

Treatment D: < >

 ${\tt N}$ = Within reference range, L = Below reference range, H = Above reference range Baseline is the last predose measurement.

Change From Baseline Table 14.3.5.14 will resemble 14.3.5.13

Table 14.3.5.13 Vital Sign Summary (Safety Population)

Page 1 of X

	Time Point		Treatment							
Vital Sign (units)		Statistic	А	В	C	D	Pooled Placebo			
Testname (unit)	Screen	n	X	X	X	Х	X			
		Mean	X.X	X.X	X.X	X.X	X.X			
		SD	X.XX	X.XX	X.XX	X.XX	X.XX			
		Minimum	XX	XX	XX	XX	XX			
		Median	X.X	X.X	X.X	X.X	X.X			
		Maximum	XX	XX	XX	XX	XX			
	Baseline	n	X	Х	X	X	X			
		Mean	X.X	X.X	X.X	X.X	X.X			
		SD	X.XX	X.XX	X.XX	X.XX	X.XX			
		Minimum	XX	XX	XX	XX	XX			
		Median	X.X	X.X	X.X	X.X	X.X			
		Maximum	XX	XX	XX	XX	XX			
	Day 1 Hour 0.	25 n	X	X	X	X	X			
	_	Mean	X.X	X.X	X.X	X.X	X.X			

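### SAP 7.5 sets negative aPTT changes from baseline to 0 before summarising; where the true change is 0 this raises the mean by about 0.40 SD and understates the SD by about 42%

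*SAP*

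**What the plan says.** SAP section 7.5 calculates, for each subject and time point, the postdose aPTT minus the predose aPTT. It then says "The mean change from baseline will be calculated using the individual change from baseline values", followed by "If change from baseline results in a negative value, this value will be set to '0' for the calculation of the summary statistics". No reason is given and no group or time point is exempt.

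The results go to the change columns of Table 14.2.3.1 and to the mean-change plots: in-text Figure 11-3 ("Arithmetic Mean aPPT Change From Baseline Versus Time Following a Single IV Infusion") and Figures 14.2.4.3 and 14.2.4.4. Table 14.2.3.1 also prints mean aPTT itself, to which the rule does not apply. The footnote specified for its shell lists treatments only and does not mention the rule.

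SAP section 8.4 covers the other laboratory changes and has no floor: "Change from baseline will be summarized in a similar manner". It keeps aPTT at the PD time points out of the laboratory summary tables, and the coagulation shell sends the reader elsewhere: "Change from baseline summaries for aPTT associated with PD time points can be found Table 14.X.X.X".

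Protocol section 12.1.6 asks only for aPTT to be listed and plotted, and specifies no floor. SAP section 9, on departures from the protocol, does not mention the rule.

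**The concern.** Assay and within-subject noise push individual changes both ways. A floor at 0 removes the downward noise and keeps the upward noise, so a group with no effect shows an average prolongation. Three groups of results are exposed: pooled placebo throughout; the 0.1 mg/kg cohort, for which Protocol section 8.4.2 expects minimal biological effect; and late time points as aPTT returns to baseline. There a reader comparing groups by eye sees a small false prolongation in placebo, SD bars that are too short, and a reduced active-placebo difference.

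The outputs would also disagree with each other. With no missing subjects, the postdose mean minus the Hour 0 mean in Table 14.2.3.1 is the signed mean change. The printed change will differ from it whenever any subject's change is negative, and nothing in the table says why. Follow-up safety aPTT under section 8.4 would be summarised by one rule and PD aPTT by another.

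**Working it through.** The plan states no figure to reproduce, so the check is of what the rule does.

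**Inputs from the documents.** The floor acts on individual changes (SAP 7.5). There are 4 active subjects per dose and 2 + 1 + 1 + 1 = 5 pooled placebo subjects (SAP section 5).

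**Assumptions.** Individual changes are normal with mean μ and SD s. The documents do not give s.

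**Formulas.** Let X ~ N(μ, s²), Y = max(X, 0) and z = μ/s, with Φ and φ the standard normal distribution function and density.

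- E[Y] = μΦ(z) + sφ(z)
- E[Y²] = (μ² + s²)Φ(z) + μsφ(z)
- Bias in the mean = E[Y] − μ
- SD after the rule = √(E[Y²] − E[Y]²)

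At μ = 0: E[Y] = 0.399s and E[Y²] = 0.5s², so SD = s√(0.5 − 0.159) = 0.584s, a loss of 41.6%.

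| True mean change | Share negative | Bias in mean | SD after rule | SD loss |
|---|---|---|---|---|
| −0.25s | 60% | 0.536s | 0.498s | 50.2% |
| −0.1s | 54% | 0.451s | 0.550s | 45.1% |
| 0 | 50% | 0.399s | 0.584s | 41.6% |
| 0.5s | 31% | 0.198s | 0.744s | 25.6% |
| 1s | 16% | 0.083s | 0.867s | 13.3% |
| 2s | 2% | 0.009s | 0.980s | 2.0% |

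**Simulation** (one million samples at each group size, μ = 0). The bias is 0.40s at n = 4 and n = 5. The average sample SD falls by 46.6% (n = 4) and 45.6% (n = 5); on the root-mean-square scale the loss is 41.6%, as in the formula.

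**Other symmetric shapes at μ = 0.** Uniform, t with 5 degrees of freedom and Laplace changes give a bias of 0.35 to 0.43 SD and an SD loss of 39% to 44%.

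**In seconds, for an assumed s of 1 to 3 seconds.** The false placebo mean is 0.399 × 1 = 0.4 to 0.399 × 3 = 1.2 seconds. With placebo truly at 0, the displayed active-placebo difference would be:

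| True difference | Shown, s = 1 | Shown, s = 2 | Shown, s = 3 |
|---|---|---|---|
| 1 second | 0.68 | 0.60 | 0.57 |
| 2 seconds | 1.61 | 1.37 | 1.26 |
| 10 seconds | 9.60 | 9.20 | 8.80 |

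**How often the rule acts.** If a share p of placebo changes is negative, the chance that at least one of 5 is altered at a time point is 1 − (1 − p)⁵. That is 83% for p = 0.3 and 97% for p = 0.5. The lower figure belongs to a true change of about 0.5s, where the bias is about 0.2s.

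**Worked example.** Five placebo changes of −2, −1, 0, 1, 2 seconds have mean 0.00, SD √(10/4) = 1.58 and minimum −2. After the rule they are 0, 0, 0, 1, 2: mean 0.60, SD √(3.2/4) = 0.89 and minimum 0.

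**The case against.** The best defence is that little depends on these numbers. SAP section 2.2 makes the PD endpoint descriptive: "aPTT values will be listed with descriptive statistics and presented graphically". The primary endpoints are adverse events, no test is planned, and the rule mostly narrows the active-placebo gap, so it does not create a drug effect. That stands, and it limits the importance of the point.

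Much of the distortion can also be undone. Unfloored aPTT means and plots are planned, and Appendices 16.2.6.4 and 16.2.6.5 give individual changes, which the rule does not clearly cover. This stands in part. The signed mean can be rebuilt from Table 14.2.3.1 if no subject is missing. The SD of change cannot be rebuilt from the two sets of summary statistics without their correlation; it needs the individual data. A reader of the table or figures is not told that any of this is necessary.

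The median is less affected. In the worked example it is 0 before and after the rule, and for normal changes at zero with n = 5 its expected bias is about 0.21 SD, roughly half that of the mean. This is correct, but the planned figures show means.

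One might argue that the drug is not expected to shorten aPTT, so negative changes are only noise. That does not justify the floor: positive noise of the same size is kept, and placebo has no drug effect to protect. The trial's own recovery criterion is two-sided, at ±10% of baseline (Protocol section 10.1). For a baseline in the 23 to 32 second reference range, that is 2.3 to 3.2 seconds either way.

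**Conclusion.** The concern holds. Followed exactly, SAP 7.5 gives biased summary statistics wherever the true aPTT change is close to 0. The headline figures, 0.40 SD for the mean and 42% for the SD, are the values at a true change of exactly 0 under normality. They are upper limits only for true changes of 0 or more; a slightly negative true change gives larger errors. The effect is negligible once the true change reaches about 2 SD. The results in SD units depend on approximate normality, to which they are not very sensitive; the results in seconds depend on an SD of change that the documents do not supply. The consequence is confined to descriptive PD displays, but the error is systematic, unexplained in the outputs and easily avoided.

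**What to change.** Delete the sentence on negative changes from SAP section 7.5. Compute n, mean, SD, SEM, minimum, median and maximum from the signed individual changes in Table 14.2.3.1 and in Figures 11-3, 14.2.4.3 and 14.2.4.4. Do the same for any summary rows in Appendix 16.2.6.4, which shares a shell that has such rows ("Tables 14.2.1.1 through 14.2.1.5 and Appendix 16.2.6.2 and 16.2.6.4 will be in the following format"). In that shell, omit CV% for change from baseline, since it has no meaning when the mean is near 0. With signed changes the bias is 0 and the SD is correct at every true change, and Table 14.2.3.1 agrees with itself when no subject is missing. If the sponsor wants a floored version as well, label it supplementary and state the rule in a footnote.

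The cost is one sentence of SAP text and one programming note. No new data are needed, and no protocol amendment, because the protocol does not specify a floor.
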